6.3 Study Endpoints

6.3.1 Primary Endpoints

Performance

Proportion (%) of patients reporting freedom from pain (pain grade 0) 2 hours post treatment without medications in at least 50% of treated attacks

6.3.2 Secondary Endpoints

Secondary Performance Endpoints

1. The proportion (%) of subjects reporting treatment response at 2 hours post treatment without rescue medications in at least 50% of treated attacks. Treatment response is defined as: pain level reduction from moderate or severe at baseline to mild or pain level of none if treatment started with mild pain
2. Proportion (%) of patients reporting, 2 hours post treatment:
 - freedom from pain (pain grade 0) and their most bothersome migraine-associated symptom (MBS) in at least 50% of treated attacks
 - freedom from nausea in at least 50% of treated attacks
 - freedom from photophobia in at least 50% of treated attacks
 - freedom from phonophobia in at least 50% of treated attacks

6.3.3 Exploratory Endpoints:

1. The proportion (%) of patients reporting freedom from pain (pain grade 0) 48 hours post treatment without medications in at least 50% of treated attacks

2. The percent of subjects who are pain-free at 2 hours with no use of rescue medication, and either have no relapse of pain within the subsequent 46 hours, or, if they have a relapse of pain in this time window, it disappears every time, after two hours, using the device, with no use of rescue medications.
3. Patient global impression of change, with emphasis on disability and quality of life.

6.3.4 Safety Endpoints:

- Treatment tolerability
- Adverse events and complications whether related or unrelated to study device.

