Objectives	
The purpose of this study is to evaluate the safety and performance of the Nerivio Migra Migraine device for the treatment of non-chronic migraine patients with and without aura

Primary Endpoint	
Primary Performance Endpoint. Proportion (%) of patients reporting freedom from pain (pain grade 0) 2 hours post treatment without rescue medications in at least 50% of treated attacks
 
Primary Safety Endpoint. Device related adverse effects

Secondary & Exploratory Endpoints	
Performance endpoints:
 
Secondary:
 
 1. The proportion (%) of subjects reporting treatment response at 2 hours post treatment without medications in at least 50% of treated attacks. Treatment response is defined as pain level reduction from moderate or severe at baseline to mild or pain level of none if treatment started with mild pain. 2. Proportion (%) of patients reporting, 2 hours post treatment: 
 ▪ freedom from pain (pain grade 0) and their most bothersome migraine-associated symptom (MBS) in at least 50% of treated attacks ▪ freedom from nausea in at least 50% of treated attacks

	
 ▪ freedom from photophobia in at least 50% of treated attacks ▪ freedom from phonophobia in at least 50% of treated attacks 
Exploratory:
 
 3. The proportion (%) of patients reporting freedom from pain (pain grade 0) 48 hours post treatment without medications in at least 50% of treated attacks 4. The percent of subjects who are pain-free at 2 hours with no use of rescue medication, and either have no relapse of pain within the subsequent 46 hours, or, if they have a relapse of pain in this time window, it disappears every time, after two hours, using the device, with no use of rescue medications. 5. Patient global impression of change, with emphasis on disability and quality of life.
Safety Endpoints	
 • Treatment tolerability • Adverse events and complications whether related or unrelated to study device.
Patient Population	Adults 18-75 years old meeting International Headache Society criteria for migraine with and without aura, who are reporting 2-8 migraine attacks per month.
Number of Patients	Up to 248 patients with evaluable data, equally distributed between US and non-US sites

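### The pain-plus-MBS secondary endpoint (section 6.3.2, item 2, first bullet) omits the primary's no-rescue condition, so as written a subject can fail the primary because of rescue and still pass it

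*Combined protocol and SAP*

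**What the plan says.** The no-medication condition appears in four of the 2-hour and 48-hour pain endpoints:

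- Primary (section 6.3.1): "2 hours post treatment without medications in at least 50% of treated attacks". Section 7.2.1 codes the variable as 1 only if the pain-free attacks were without rescue.
- Secondary 1 (section 6.3.2): "The proportion (%) of subjects reporting treatment response at 2 hours post treatment without rescue medications in at least 50% of treated attacks".
- Exploratory 1 (section 6.3.3): "48 hours post treatment without medications in at least 50% of treated attacks".
- Exploratory 2 (section 6.3.3): "pain-free at 2 hours with no use of rescue medication".

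It is absent from secondary item 2. The stem is "Proportion (%) of patients reporting, 2 hours post treatment" and the first bullet is "freedom from pain (pain grade 0) and their most bothersome migraine-associated symptom (MBS) in at least 50% of treated attacks". The three single-symptom bullets have the same form, for example "freedom from nausea in at least 50% of treated attacks" and, in the Synopsis, "freedom from photophobia in at least 50% of treated attacks".

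Section 6.1 asks patients to avoid rescue before treatment and for the first two hours after it, and to record any use if they cannot. The 2-hour screen (section 6.4.2.2) collects rescue use as yes/no with the drug name. Section 7.8.2.2 places the secondary endpoints behind the primary in a hierarchy meant to control type I error.

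**The concern.** The first bullet requires pain grade 0 at 2 hours, which is the primary's own component, plus freedom from the most bothersome symptom (MBS). It should therefore be at least as hard to meet as the primary. Without the rescue condition it is not: an attack that counts against the subject in the primary because rescue was taken can count in favour here.

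A confirmatory claim may rest on this endpoint. If rescue-settled attacks count as successes, the result no longer describes the device alone, and the difference between arms then depends on how much rescue each arm used. If sham patients use more, a real effect is diluted; if active patients used more, the shift would go the other way.

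**Working it through.** **1. Does any other text supply the rule?**

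- Section 7.2.2 says the secondary endpoints are binary variables represented as the primary is. That fixes the 0/1 form; it names no rescue rule.
- Section 6.4.3 treats rescue as failure, but only for sustained relief over 48 hours.
- Section 6.1 and the Synopsis expect some rescue before 2 hours and have it recorded. Neither removes such attacks from the treated attacks nor says how to score them.
- Section 7.8.5 (count, percentage, chi-squared test) and section 7.8.7 (missing data) add no rule. The per-protocol analysis in section 7.7.4 is planned for the primary only.

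So the gap stands on the text. That a subject can fail the primary and pass the composite follows from the definitions and needs no assumed figure.

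**2. The plan's own figure.** Section 7.4: 30% versus 10%, 80% power, two-sided 5%, 1:1. With pooled variance under the null:

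n per arm = [1.96·√(2·0.2·0.8) + 0.842·√(0.3·0.7 + 0.1·0.9)]² / 0.2² = 61.6, so 62 per arm and 124 in total. Power at 62 per arm is 80.3%. The stated figure is reproduced.

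**3. Illustration for the composite.** Assumptions, none given in the documents: four independent attacks per subject; MBS freedom accompanies every pain-free attack; rescue is used only in attacks the device did not settle; a share h of rescue-treated attacks is pain-free by 2 hours.

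Subject success means at least 2 of 4 attacks: R(p) = 1 − (1−p)⁴ − 4p(1−p)³. Solving R(p) = 0.30 and 0.10 gives per-attack rates of 0.272 (active) and 0.143 (sham). As written, the per-attack rate becomes p + h × rescue share; with the condition it stays p.

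Power = Φ{[Δ − 1.96·√(2p̄(1−p̄)/62)] / √[(p_a(1−p_a) + p_s(1−p_s))/62]}.

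| Rescue, active vs sham | Subject rates as written, h = 0.5 | Power, h = 0.5 | Power, h = 0.25 |
|---|---|---|---|
| With the condition (any rescue rate) | 30.0% vs 10.0% | 80% | 80% |
| 10% vs 10% | 38.8% vs 16.9% | 78% | 79% |
| 10% vs 20% | 38.8% vs 24.9% | 38% | 60% |
| 10% vs 30% | 38.8% vs 33.5% | 9% | 39% |

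For the third row at h = 0.5: per-attack rates are 0.272 + 0.05 = 0.322 and 0.143 + 0.10 = 0.243; the numbers in the power formula are (0.1387 − 0.1640)/0.0827 = −0.306, which gives 38%. In that row about 38.8 − 30.0 ≈ 9% of active and 24.9 − 10.0 ≈ 15% of sham subjects fail the primary yet pass the composite.

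With beta-binomial attacks (within-patient correlation 0.3, h = 0.5; per-attack rates re-solved to 0.259 and 0.096), the three as-written powers are 75%, 42% and 16%.

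**4. The three single-symptom endpoints.** Assume the symptom is present in f = 0.7 of attacks, there is no device effect (resolution r = 0.3 in both arms), no new symptoms emerge, h = 0.5, and rescue share s is the same in symptom-absent attacks. Per-attack success is f(r + 0.5s) + (1 − f) as written and fr + (1 − f)(1 − s) with the condition.

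| Rescue, active vs sham | As written: subject rates | As written: sham wins | With condition: subject rates | With condition: active wins |
|---|---|---|---|---|
| 10% vs 20% | 75.2% vs 79.7% | 9% | 65.7% vs 60.9% | 8% |
| 10% vs 30% | 75.2% vs 83.8% | 22% | 65.7% vs 55.9% | 20% |

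The nominal rate for each direction is 2.5%. As written, false wins for active are below 1% in both rows. Either scoring is biased when rescue differs by arm, in opposite directions.

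**The case against.** The strongest objection is that section 7.2.2 can be read as carrying over the primary's condition, since the primary variable is defined just above it with that condition. A separate statistical analysis plan, mentioned in sections 6.2, 7.8 and 9, may also state the rule. The first reading is possible, but the sentence speaks only of binary form. The second would settle the matter by cross-reference. Both are reasons to write the rule down, and both limit the claim to how the endpoint reads as written.

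A reader might infer that all four item-2 endpoints need the condition. The documents do not support that. Only the first bullet contains pain grade 0, so only there does the inconsistency with the primary arise. For the other three, leaving rescue out of the definition and reporting it by arm is defensible, and step 4 shows that adding the condition can produce false wins for the device.

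The sizes are also open to challenge. They rest on assumed rescue rates, give every subject four attacks although the stage can end earlier, ignore a possible increase to 248, and are not conditional on the primary succeeding, although the hierarchy tests secondaries only then. This stands: the powers are illustrations and do not predict the planned test.

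**Conclusion.** The pain-plus-MBS endpoint lacks a condition it needs to be consistent with the primary, and no other text in the document clearly supplies it. That conclusion rests on the definitions alone. How much it matters depends on rescue use, for which the documents give no rates: very little if use is equal between arms (78% against 80% power at 10% each), and a lot if sham patients use twice as much (38%), under the assumptions listed above.

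A reader might infer that the omission flatters the device. The documents do not fix a direction: more rescue in sham dilutes the composite contrast, and more in active would do the reverse. Nor are the primary endpoint or the 124 affected.

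For nausea, photophobia and phonophobia the point is narrower: the scoring of rescue-treated attacks should be stated in advance, because either choice can mislead if rescue differs by arm.

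**What to change.** 1. Add the no-rescue condition to the pain-plus-MBS bullet in section 6.3.2 and in the Synopsis. A treated attack with rescue taken within 2 hours of treatment start then counts as a failure, using the rescue item already on the 2-hour screen. That screen lists no time of intake and late reports are chased by query and telephone, so for late reports confirm that the rescue was taken within the 2 hours. If a separate analysis plan already states the rule, a cross-reference is enough.
2. For nausea, photophobia and phonophobia, state before any unblinded look whether rescue-treated attacks can count as successes. Report the other scoring as a sensitivity analysis and show rescue use by arm beside the results; section 7.8.5 already plans that summary.
3. Clarification only: say where the MBS is recorded. The PRO screens in section 6.4.2 show no such item, but the eCRF list is in the Data Management Plan.
4. Optional: an added analysis of each symptom restricted to attacks that had it at treatment start. It selects on post-randomisation status and drops subjects who never have the symptom.

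The cost is wording, one sensitivity analysis per symptom endpoint, and a timing check on late reports. The sample size does not change.

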Study Procedures	
Following successful screening, enrollment interview and signing of informed consent, participants will be provided with an active Nerivio Migra or identically looking sham device and trained to perform treatment and provide feedback via the smartphone application.
 
Baseline information including mean frequency and severity of migraine attacks, occurrence of other headaches, presence of ICHD-3 diagnostic criteria for migraine with and without aura and use of preventive and rescue medications will be recorded.
 
During roll-in stage, migraine status will be recorded and participants will be requested to complete a quality of life questionnaire.
 
Participants who successfully completed the roll-in stage will continue to the stage involving treatment of four qualifying migraine attacks. A qualifying migraine attack shall be preceded by at least 48 hours of freedom from headache. Participants will be instructed to activate the device at the onset of a qualifying migraine attack and manually adjust stimulation intensity to a level within the pre-defined range where it is perceivable but not painful. Patients will be requested to refrain from use of rescue medications prior to and during the first two hours after treatment with the device, and if they can not comply with this, record their use of medications in the smartphone application. Via the application, each participant will be asked to rate his/her migraine pain level using Pain Grades Scale with values 0-3 (no pain, mild, moderate, severe): (1) upon starting the treatment, (2) two hours after starting treatment, (3) 48 hours after start of the first treatment corresponding to current migraine attack. Participants will be also asked to provide feedback using the application regarding the time elapsed from start of migraine attack to start of the treatment. In addition, participants will be reporting their use of rescue medication and presence of nausea, photophobia, phonophobia and allodynia, as well as additional migraine symptoms.
 
In case of failure to provide feedback regarding pain level post-treatment, queries will be generated via EDC system and telephone follow-up will be performed by study investigator staff to solicit such feedback. After providing feedback at two hours post start of treatment and in case of pain recurrence, participants will be allowed to re-treat the attack using Migra device.
 
Adverse events will be reported.
 
Post study questionnaire will include patient global impression of change, blinding and usability assessments.

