6.4.1 Types of Data

Overall, data collected in the course of the study may be divided into three categories:

1. captured by clinical personnel. This includes demographic characteristics, baseline migraine parameters, end of study questionnaires, adverse events reports. Source data may be paper worksheets, further transferred into eCRFs maintained by the EDC system.
2. patient reported outcomes. This includes feedback entered via the smartphone application regarding migraine pain level, migraine symptoms, treatment perception, rescue medications. These data are used for calculation of study endpoints. Here, source data will be electronic, followed by automatic transfer to eCRFs.
3. additional information and technical data, captured by means of a system of log files by the Application. This includes stimulation activation times, applied stimulation intensity, device defects information, and other.

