6.4.2.1 Start attack/episode PRO feedback data

The screen provides for collection of the following data:

Item	Description	Control type	Values range
Current migraine pain level	Current migraine pain level in pain grade categories	Dropdown list	Mild (1), Moderate (2), Severe (3).

Time from onset of migraine pain	Time from onset of migraine pain	Dropdown list	under 10 minutes 10-20 minutes 20-60 minutes 1-2 hours 2-4 hours over 4 hours
Nausea	Presence of nausea	Radio buttons	Y/N
Sensitivity to light	Presence of photophobia	Radio buttons	Y/N
Sensitivity to sound	Presence of phonophobia	Radio buttons	Y/N
Increased skin sensation	Presence of allodynia	Radio buttons	Y/N

6.4.2.2 2h PRO

This feedback dialog appears 2h after the treatment program has started.

The screen provides for collection of the following data:

Item	Description	Control type	Values range
Current migraine pain level	Current migraine pain level in pain grade categories	Dropdown list	No pain (0), Mild (1), Moderate (2), Severe (3).
Medication	Whether rescue medication was taken	Radio buttons	Y/N
Medication name	Rescue medication	Dropdown list	From a pre-defined list
Nausea	Presence of nausea	Radio buttons	Y/N
Sensitivity to light	Presence of photophobia	Radio buttons	Y/N
Sensitivity to sound	Presence of phonophobia	Radio buttons	Y/N

Increased skin sensation	Presence of allodynia	Radio buttons	Y/N
Arm side where device was applied	Left or right arm	Radio buttons	L/R
Pain location (side)		Dropdown list	L R both
Additional feedback	Additional, free style feedback	Textbox	Free text, optional

6.4.2.3 48h PRO

The screen shall provide for collection of the following data:

Item	Description	Control type	Values range
Current migraine pain level	Current migraine pain level in pain grade categories	Dropdown list	No pain (0), Mild (1), Moderate (2), Severe (3).
Medication	Whether rescue medication was taken	Radio buttons	Y/N
Medication name	Rescue medication	Dropdown list	From a pre-defined list
Additional feedback	Additional, free style feedback	Textbox	Free text, optional

6.4.3 *Methods and Timing of Assessing, Recording and Analyzing Variables*

Once the last patient will have completed the study and all the queries have been resolved, database will be locked, cleaned and exported for final statistical analysis. Study report will be issued following final database lock.

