7 STATISTICAL CONSIDERATIONS

7.1 *Study Design and Aim*

The study is designed as a prospective, randomized, double-blind, sham controlled multi-center clinical trial. The study aim is to demonstrate safety and effectiveness of Nerivio Migra electro stimulation device for treatment of migraine attacks with and without aura.

7.2 *Study Variables*

7.2.1 *Primary performance variable*

The primary performance endpoint, the proportion (%) of patients reporting freedom from pain (pain grade 0) 2 hours post treatment without rescue medications in at least 50% of treated attacks, will be measured in the form of a binary variable which will be assigned the value of "1" if the subject reports freedom from pain (pain grade 0) 2 hours post treatment without rescue medications in at least 50% of his/her treated attacks, and "0" otherwise.

7.2.2 *Secondary performance variables*

The secondary performance endpoints will all be expressed in the form of binary variables as in the representation of the primary performance variable.

7.2.3 *Exploratory performance variables*

The exploratory performance endpoint, the proportion (%) of patients reporting freedom from pain (pain grade 0) 48 hours post treatment without rescue medications in at least 50% of treated attacks, will be measured in the form of a binary variable which will be assigned the value of "1"

if the subject reports freedom from pain (pain grade 0) 48 hours post treatment without rescue medications in at least 50% of his/her treated attacks, and “0” otherwise.

Patient global impression of change is measured via a questionnaire.

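### No itemised screen, baseline list or questionnaire identifies the most bothersome symptom, and the MBS is undefined, so the pain-plus-MBS secondary endpoint is only partly determinable from the listed data

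*Combined protocol and SAP*

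**What the plan says.** The endpoint is the first bullet of secondary endpoint 2 in the Synopsis and in Section 6.3.2. It is a patient-level proportion, assessed two hours after the device is used: "freedom from pain (pain grade 0) and their most bothersome migraine-associated symptom (MBS) in at least 50% of treated attacks". These are the only two places where the MBS is mentioned.

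Section 7.2.2 sets the coding: "The secondary performance endpoints will all be expressed in the form of binary variables as in the representation of the primary performance variable". Each patient is therefore a 1 or a 0, according to whether at least half of the treated attacks succeed.

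Section 6.4.1 names app-entered patient reports (pain level, symptoms, treatment perception, rescue medication) as the source: "These data are used for calculation of study endpoints". Sections 6.4.2.1 to 6.4.2.3 then itemise three screens. The Synopsis describes the same capture in prose: "participants will be reporting their use of rescue medication and presence of nausea, photophobia, phonophobia and allodynia". That sentence goes on to mention additional migraine symptoms, without naming or ranking them.

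**The concern.** To score an attack on this endpoint, one must know which symptom was the patient's most bothersome and whether it was gone at 2 hours. The listed data give presence or absence of four symptoms but do not say which one matters. If no MBS item is collected, someone must later choose a substitute: any starting symptom cleared, all of them cleared, or the patient's recollection once the outcome is known. The first two give different answers for the same partly cleared attack, and recall may be coloured by what resolved.

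The endpoint is one of five secondary endpoints, and Section 7.8.2.2 tests these after the primary within the hierarchy meant to control type I error. A component whose definition is settled after the data are in weakens that control. An answer not asked for at the time cannot be faithfully recovered afterwards.

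**Working it through.** The plan gives no figure for this endpoint to reproduce. The check is a trace of the listed data, followed by a count of what can be deduced without an MBS item.

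**1. Where the MBS could be recorded.**

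| Place | What it lists | Identifies the MBS? |
|---|---|---|
| 6.4.2.1, start screen ("The screen provides for collection of the following data") | Pain grade; "Time from onset of migraine pain"; yes/no for nausea, light, sound, skin sensitivity | No |
| 6.4.2.2, 2h screen ("This feedback dialog appears 2h after the treatment program has started") | Pain grade, medication and its name, the same four yes/no items, arm side, pain side, optional free text | No |
| 6.4.2.3, 48h screen ("The screen shall provide for collection of the following data") | Pain grade, medication and its name, optional free text | No |
| Baseline lists (Synopsis; 6.1) | Attack frequency and severity, other headaches, ICHD-3 criteria, preventive and rescue medication | No |
| Screening and end-of-study visits (6.6.2) | Histories, medication, training, questionnaire, adverse events | No |
| Appendix B, start and end questionnaires | Disability, quality of life, spending, usability, local skin effects | No |

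That is 0 of 3 screens and 0 of 2 questionnaires. The analysis text (7.2.2, 7.8.5, 7.8.7) has no derivation rule either.

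**2. What can be deduced for one attack.** Assume the MBS is one of the recorded symptoms present at start.

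- Pain at 2 hours: failure, whatever the MBS.
- Pain-free, all starting symptoms gone: success.
- Pain-free, all starting symptoms still present: failure.
- Pain-free, some starting symptoms gone and some remaining: undetermined.
- Pain-free, no symptom at start: no candidate MBS, and no rule.

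With a single starting symptom, only the second and third pain-free cases can arise, so status is known.

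**3. Count of patterns in a pain-free attack.** With k recorded symptoms, each yes or no at start and at 2 hours, there are 4^k patterns.

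- No candidate: 2^k.
- Known success: 3^k − 2^k. Known failure: the same number.
- Undetermined: 4^k − 2(3^k − 2^k) − 2^k = 4^k − 2·3^k + 2^k.

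| | k = 3 (nausea, light, sound) | k = 4 (allodynia added) |
|---|---|---|
| Total | 64 | 256 |
| No candidate | 8 | 16 |
| Known success | 27 − 8 = 19 | 81 − 16 = 65 |
| Known failure | 19 | 65 |
| Undetermined | 64 − 54 + 8 = 18 | 256 − 162 + 16 = 110 |

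These count logical possibilities, not frequencies. The documents give no symptom distribution from which to weight them.

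**4. Effect on one patient (illustration).** Suppose four treated attacks: two with pain at 2 hours, one pain-free with all starting symptoms gone, and one pain-free with photophobia gone but nausea remaining. The success share is 1/4 = 25% if nausea was the MBS in the last attack and 2/4 = 50% if photophobia was. The patient is a non-responder in the first case and a responder in the second, on identical recorded data. Scoring by any symptom cleared gives responder; scoring by all symptoms cleared gives non-responder.

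**The case against.** The strongest reply is that the documents do not claim to list everything collected. Section 6.4 places the list and structure of the eCRFs in the Data Management Plan, which is not supplied. Section 6.4.2 describes itself as an overview. The roll-in diary and the migraine history taken at screening are not itemised. The listings are visibly incomplete elsewhere: additional symptoms (Synopsis; 6.6.1) and treatment perception (6.1) have no dedicated field on the screens, and the global-impression and blinding items promised for the end of study do not appear in the Appendix B text. The endpoint's wording also allows the MBS to be a patient-level attribute, which would sit on a baseline form rather than an attack screen. All of this stands. It means a field may exist, but it does not supply the missing definition, timing or no-symptom rule. Section 9 adds that case report forms and the Data Management Plan lie outside the protocol and can change without amending it, so a field held only there is not fixed by the protocol.

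A second reply is that much of the endpoint can still be scored. This also stands: every attack with pain at 2 hours is a known failure, and many pain-free attacks are determined.

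The missing-data provisions of Section 7.8.7 do not close the gap. The sensitivity and worst-case analyses are framed for the primary endpoint, and imputation of secondary endpoints is only a possibility. Neither identifies the MBS.

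**Conclusion.** The point holds for the listed data. The protocol neither defines the MBS nor shows where it is captured, so this secondary endpoint can be bounded but not computed as defined. Lower and upper bounds come from scoring every undetermined attack as a failure or as a success; no-symptom attacks need their own rule first.

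A reader might infer that the endpoint is lost, or that it cannot be computed from what the trial actually collects. The documents do not support that: the eCRF list is not supplied, and a large part of the attack-level status follows from pain and the recorded symptoms. A reader might also infer that the MBS has to be named before each treatment. No section says so; selection per attack and selection once per patient are both open.

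The pattern counts assume that the MBS is one of the recorded symptoms and was present at start. If it may be one of the unlisted additional symptoms, or a fixed patient-level symptom absent at the start of a given attack, even single-symptom or fully cleared attacks are not settled. The share of attacks affected cannot be derived from the documents. The other four secondary endpoints, the primary endpoint and the sample size are untouched.

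**What to change.** Before any attack is treated:

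1. Add one item identifying the MBS. Two options are a dropdown on the start-of-attack screen limited to the symptoms marked present, or a single baseline item. If a field already exists in the Data Management Plan, cite it in Section 6.3.2 instead.
2. State whether the MBS is fixed per patient or chosen per attack, when it is recorded, and which symptoms are eligible. Any eligible symptom needs a 2-hour field.
3. Define attack-level success as pain grade 0 and that symptom answered No on the 2-hour screen.
4. Give an explicit rule for attacks with no associated symptom at start and, if the MBS is fixed per patient, for attacks in which it is absent at start. If such attacks are left out, say openly that the denominator is no longer all treated attacks, as Section 6.3.2 now has it.

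The cost is a small change to the sponsor's own app and a few lines in the endpoint definition. The patient spends a few seconds more per attack, or answers one extra question at baseline.
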